Theranova, LLC

CLINICAL STUDY PROTOCOL – TNV-0514-WVD; CRD-09-1105

NCT03688282

Wearable Vibration Device to Prevent Bone Loss in Postmenopausal Women – Aim 2

Protocol Summary

Title	Wearable Vibration Device to Prevent Bone Loss in Postmenopausal Women– Aim 2
Sponsor	Theranova, LLC
Device	Wearable Vibration Device (WVD)
Background and Rationale	An emerging alternative to pharmacological interventions for osteoporosis is whole-body vibration (WBV). The wearable vibration device (WVD) aims to consistently deliver vibrations directly to the hip and spine and allowing use during many everyday activities. We propose that demonstrating higher rates of compliance and consistent delivery of optimal force with accelerometer-based force feedback will provide a superior alternative to WBV platforms and is plausibly more effective at preventing bone loss in postmenopausal women than vibration platforms in the home setting.
Objectives.	To demonstrate that postmenopausal women will: 
1. Tolerate our device;2. Receive consistently therapeutic levels of vibration; and3. See changes in bone turnover.
Indications for Use/Patient Population	The device is to be worn by women who are postmenopausal to deliver vibration to the hips and spine to prevent bone loss. Subjects will be instructed to wear the device 30 minutes while walking or standing.
Trial Design	Single center prospective, non-randomized, unblinded, Non-Significant Risk (NSR) trial.
Study Population	Postmenopausal women
Number of Subjects	Up to 24
Number of Sites	1

Study Flow Outline Revised

Recruitment and Screening	Baseline Visit (Office Visit #1)				Intervention Assessment (Office Visit #2)					
Contact Interested Subjects Determine Eligibility Schedule Baseline Visit	Enrollment Consent	Fit Device Pre-Activity Blood Draw	30 Min Self-Selected Activity (WVD Motor Off)	Wait 30 Minutes Patient Questionnaires	Post Activity Blood Draw	Fit Device Pre-Activity Blood Draw	30 Min Self-Selected Activity (WVD Motor On)	Wait 30 Minutes Patient Questionnaires	Post Activity Blood Draw	Process Payment
	Internal Control Acute assessment of bone marker with no vibration stimulus.				Treatment Acute assessment of bone marker with 30 minute vibration.					

Study Procedures

Screening Period (Ongoing)

Potential subjects will answer screening questions via phone to determine eligibility. Women who qualify based on screening criteria will be scheduled for a baseline visit at the University of Nebraska Medical Center. Subjects with low or normal bone mass may be enrolled in the study.

Study Period (1-2 weeks)

The two week protocol consists of subjects: 1) visiting the clinic for a Wearable Vibration Device (WVD) pack fitting, wearing the device (motor off) for 30 minutes while standing or walking, and completing a pre-post activity blood draw, 2) visiting the clinic at the end of week one to measure acceleration, wear the device (motor on) for 30 minutes while standing or walking, and complete a pre-post activity blood draw.

Safety & Safety Monitoring

It is the responsibility of the investigator to report when an adverse event has occurred. Adverse event information will be collected throughout the study. Adverse Events (both expected and unexpected) will be recorded and reported appropriately.

Inclusion Criteria

1. Female
2. Last menstrual period at least one year and not more than six years.
3. 19 years of age and older.
4. BMD T-score at or above -2.5 at the total hip and L1-L4 spine skeletal sites as measured by DXA.
5. Ambulatory (can walk or stand without an assistive device for a minimum of 30 minutes).
6. Able to understand spoken and written English.
7. Capable and willing to follow all study-related procedures.

Exclusion Criteria	
 1. BMD T-score at or below -2.49 at the total hip and L1-L4 spine skeletal sites as measured by DXA. 2. A 10-year probability of hip fracture > 3% or major fracture or > 20% based on results of DXA using the FRAX tool (see attached). 3. Weight > 300 lbs. 4. Are currently taking or have taken bisphosphonates within the past 6 months, estrogen replacement therapy, or drugs affecting bone such as tamoxifen or aromatase inhibitors within the past 6 months. 5. Active cancer or cancer treatment. 6. Any change in Calcium or Vitamin D supplementation within the last 3 months. 7. Any change in exercise in the past 6 months. 8. Fractures or major surgery within the past 6 months. 9. Medical Implants (excluding dental implants). 10. Diagnosed with Paget's disease, heart disease, uncontrolled hypertension, renal disease, chronic fatigue syndrome, herniated disc, severe peripheral neuropathy, severe osteoarthritis. 11. Any bleeding disorder or treatment with a blood thinning medication within the last 2 years.
Statistical Analysis	
This study is observational, is not statistically powered and no formal statistical analyses are planned. Data will be listed by subject; treatment number, and subject tolerability during treatment.

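### Activity is self-selected at both the motor-off and motor-on visits, so a woman who switches between standing and walking has an on-versus-off marker change that mixes vibration with activity

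*Protocol*

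**What the plan says.** In the Study Flow Outline, office visit 1 is headed "Internal Control Acute assessment of bone marker with no vibration stimulus" and office visit 2 "Treatment Acute assessment of bone marker with 30 minute vibration". Each visit has a blood draw before the activity and another after a 30-minute wait. The activity cell reads "30 Min Self-Selected Activity (WVD Motor Off") at visit 1 and "30 Min Self-Selected Activity (WVD Motor On") at visit 2.

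The Study Period section gives the permitted activities for each visit separately: "wearing the device (motor off) for 30 minutes while standing or walking" for the first and "wear the device (motor on) for 30 minutes while standing or walking" for the second. The Indications for Use row matches this: "Subjects will be instructed to wear the device 30 minutes while walking or standing".

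The third objective is to show changes in bone turnover. The Statistical Analysis row states: "This study is observational, is not statistically powered and no formal statistical analyses are planned". It then lists data by subject, treatment number and tolerability, and does not name the activity performed.

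**The concern.** The control condition is not rest. It is 30 minutes of activity wearing the device with the motor off. Such a control serves to separate the effect of vibration from whatever activity and wear do on their own. For a given woman it does so only if the activity is the same at both visits.

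The protocol leaves the activity free each time. A woman may stand with the motor off and walk a week later with the motor on, or the reverse. Her on-versus-off difference then has two possible explanations. The motor-off visit is the only control the protocol names for the bone turnover objective, so this ambiguity falls on the one comparison available for it.

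**Working it through.** The protocol states no figure to reproduce. The check is a reading of the text, some simple algebra, and an illustration with assumed inputs.

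**Reading.** The self-selected label appears at both visits, and the choice of standing or walking is stated for each. No sentence in the protocol asks a woman to repeat her visit 1 activity. The pre-activity draw at each visit removes a difference in starting level between visits, but not a difference in response to walking versus standing.

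**Algebra.** For each woman, take the post-minus-pre marker change at the motor-on visit minus that at the motor-off visit. Let V be the vibration effect and w the walking-minus-standing effect on the marker change, and assume the two add. Apart from random variation, her difference is:

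- same activity at both visits: V
- stands at visit 1, walks at visit 2: V + w
- walks at visit 1, stands at visit 2: V − w

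Suppose that, of n women, a switch from standing to walking and b from walking to standing. Measure w in SDs of the within-woman difference without switching, so that this SD is 1. Then:

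- shift in the mean difference = (a − b)/n × w
- SD of the difference = √(1 + [(a + b)/n − ((a − b)/n)²] × w²)

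**Inputs.** From the protocol: enrolment is up to 24. Assumed, because the protocol does not give them: a, b, w, and n = 12 as a smaller enrolment.

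| n | a, b | Quantity | w = 0 | w = 0.2 | w = 0.5 | w = 1 |
|---|---|---|---|---|---|---|
| 24 | 0, 0 | mean shift | 0 | 0 | 0 | 0 |
| 24 | 1, 0 | mean shift | 0 | 0.008 | 0.021 | 0.042 |
| 24 | 3, 0 | mean shift | 0 | 0.025 | 0.0625 | 0.125 |
| 24 | 3, 3 | mean shift | 0 | 0 | 0 | 0 |
| 24 | 3, 3 | SD | 1 | 1.005 | 1.031 | 1.118 |
| 12 | 3, 0 | mean shift | 0 | 0.05 | 0.125 | 0.25 |
| 12 | 3, 3 | SD | 1 | 1.010 | 1.061 | 1.225 |

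Two cells written out for w = 1 and n = 24: with 3 net switchers the shift is 3/24 × 1 = 0.125; with 3 each way the SD is √(1 + 6/24) = √1.25 = 1.118.

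**Scale.** With SD 1, the standard error of the mean difference is 1/√24 = 0.204 for n = 24 and 1/√12 = 0.289 for n = 12. Taking 3 net switchers and w = 1, the shift is 0.125/0.204 = 0.61 standard errors for n = 24 and 0.25/0.289 = 0.87 for n = 12. At w = 0.2 it is 0.025/0.204 = 0.12 and 0.05/0.289 = 0.17. In the individual listing, a switcher's own difference is off by the full w, whatever n is.

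**The case against.** The strongest reply is that no harm is shown. The marker is not named, nothing in the protocol says that 30 minutes of walking rather than standing would move it, and nothing says that any woman will switch. Every input to the illustration other than the upper enrolment limit is assumed, and for small w the shifts are well below one standard error. With no formal analysis and no planned mean or SD, what is left is how one reads the listings of individual switchers. All of this stands, and it limits the point to a minor one.

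It can also be said that the free choice is deliberate, matches the intended use and suits the tolerability and vibration-delivery objectives. That is right, and it is a reason to leave visit 1 free. It is not a reason to leave visit 2 free of visit 1, since both activities would still be represented across women. If vibration itself led a woman to change activity, that would be worth knowing, and recording departures would keep most of that information.

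Recording the activity without requiring a match would flag the switchers, and the comparison could be read in the others. This recovers much of the interpretation, but the switchers' own contrasts remain mixed. An analysis plan could describe or stratify by activity; it could not make a woman's two visits alike afterwards. Site instructions not shown here may already hold activity constant. If so, the protocol only needs to say so.

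Finally, matching activity leaves other limitations in place: the fixed off-then-on order, the lack of blinding, and differences in pace or in the mix of standing and walking. These are separate, and do not justify keeping one that is easily removed.

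**Conclusion.** The point holds as a minor design weakness. As written, the plan lets activity differ between a woman's control visit and her treatment visit, so a switcher's on-versus-off change cannot be attributed to vibration alone. The bias in a mean would be the net share of switchers times the activity effect. Both quantities are unknown, so neither size nor direction can be stated, and the bias and added spread are zero if no one switches or if activity does not affect the marker. The algebra assumes that vibration and activity effects add. This is an avoidable ambiguity in the only named control for the bone turnover objective, not a demonstrated bias.

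**What to change.** In the Study Period section, keep the free choice of standing or walking at visit 1 and record it. Add one sentence requiring the same activity for the 30 minutes at visit 2, with any departure recorded, and include the activity at each visit in the subject listing.

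The cost is that sentence and one recorded item per visit; no extra visit, blood draw or subject is needed. The downside is less freedom at visit 2, though no woman is asked for an activity she has not already done at visit 1.

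### Does settling eligibility by phone leave the DXA and FRAX criteria unapplied?

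*Protocol*

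**What the plan says.** Under Screening Period (Ongoing), "Potential subjects will answer screening questions via phone to determine eligibility", and then "Women who qualify based on screening criteria will be scheduled for a baseline visit at the University of Nebraska Medical Center". The Study Flow Outline gives the same order in its recruitment column: "Contact Interested Subjects Determine Eligibility Schedule Baseline Visit". Consent comes next, at office visit 1, followed by device fitting and the first blood draw.

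Three numbered criteria rest on a bone scan:

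- Inclusion 4: "BMD T-score at or above -2.5 at the total hip and L1-L4 spine skeletal sites as measured by DXA".
- Exclusion 1: "BMD T-score at or below -2.49 at the total hip and L1-L4 spine skeletal sites as measured by DXA".
- Exclusion 2: ten-year fracture probabilities above 3% (hip) or 20% (major), "based on results of DXA using the FRAX tool (see attached").

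Under Study Period, visit 1 consists of "visiting the clinic for a Wearable Vibration Device (WVD) pack fitting, wearing the device (motor off) for 30 minutes while standing or walking", with blood drawn before and after. Visit 2 consists of "visiting the clinic at the end of week one to measure acceleration, wear the device (motor on) for 30 minutes while standing or walking", again with paired draws. The word DXA occurs only in the eligibility criteria.

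**The concern.** A phone answer cannot supply T-scores at two named skeletal sites, one of them with a cut-off given to two decimals, nor a fracture probability derived from a scan. If the phone call really is the whole eligibility decision, three criteria have no point at which they are applied, and a woman could reach device fitting with her bone density unknown to the site.

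At stake would be whom the results describe. The trial enrols up to 24 women and lists data by subject, so at full enrolment each wrongly entered woman is 1/24, or about 4.2%, of the data set. Exposing women whom the fracture-risk exclusion was meant to keep out would also matter in its own right.

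**Working it through.** The protocol gives no figure on this point to reproduce, and no formula applies. The check is to compare each DXA-dependent criterion with each described step.

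**Criteria.** There are 7 inclusion and 11 exclusion items, 18 in all. Three of them cite DXA.

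| Criterion | Value needed | Basis stated in the criterion |
|---|---|---|
| Inclusion 4 | T-scores, total hip and L1-L4 | Measured by DXA |
| Exclusion 1 | T-scores, same sites | Measured by DXA |
| Exclusion 2 | FRAX 10-year probabilities | Computed from DXA, tool attached |

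**Steps.**

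| Stage | Described content | DXA or FRAX named? |
|---|---|---|
| Phone screening | Questions, eligibility, scheduling | No |
| Visit 1 | Consent, fitting, blood draws, 30 minutes motor off, wait and questionnaires | No |
| Visit 2 | Fitting, acceleration, blood draws, 30 minutes motor on, wait and questionnaires, payment | No |

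So three criteria need a scan result and none of the described steps names one. The factual basis of the concern is correct.

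**Does enrolment on unmeasured values follow?** No, for two reasons.

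1. The criteria fix the standard of evidence. A recalled or guessed T-score is not one measured by DXA, and FRAX cannot be run on DXA results unless someone holds those results. The document nowhere permits self-report. A woman without a scan result has not been shown to meet inclusion 4 and cannot be cleared on exclusion 2.
2. The procedural text does not limit screening to a conversation. It calls the screening period ongoing, makes qualification depend on the screening criteria, and places consent and enrolment at visit 1. Asking for a report during screening, or checking it at visit 1, is consistent with every sentence.

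**What if a check came late?** Visit 1 runs with the motor off, and vibration is first delivered at visit 2, at the end of week one. A woman found ineligible after visit 1 has had the device fitted, activity and blood draws but no vibration. The total planned vibration exposure is one 30-minute session, in a trial classed as non-significant risk.

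**What happens to the results?** Write *d* for a woman's pre-to-post change with the motor on minus her change with the motor off. Both changes come from the same woman, at visits about a week apart, so a misjudged T-score affects whether she is in the set, not how *d* is formed. The Statistical Analysis section says that the study is not powered and plans no formal analysis, so there is no error rate or power for such an error to disturb. Its effect is on the description of the population.

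**The case for a change.** The strongest case for acting is that the protocol does address how eligibility is decided, and assigns it to a contact that cannot settle three of its own criteria. A SAP would not repair that. Other exclusions carry explicit look-back periods (3 months, 6 months, 2 years), whereas the DXA has none. Since women may be only one year past their last period, an undated scan could even predate menopause. A clarifying line would cost almost nothing.

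Part of this stands. The text is silent on the source, timing and permissible age of the scan, and scan age is the element on which two careful sites could differ. But there is one site, the text at hand is a condensed summary, and collecting reports is routine screening paperwork. The document also gives no basis for choosing a particular scan window, so a review cannot say that a given age would be wrong.

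The argument that the bone-density criteria go unapplied does not stand, because it sets the phone sentence above criteria that explicitly require measurement. Nor does the document rank these criteria above its other exclusions, such as implants, recent fracture or surgery, and heart disease.

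**Conclusion.** No change to the plan follows. This is missing operational detail that site staff would fill sensibly. The phone wording is loose, but the criteria already require DXA-based values for every woman, and a reader who applies all 18 items must obtain them.

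The gap covers three criteria and up to 24 women. The share who might be misclassified cannot be derived from the document, and no figure is offered. The motor-off versus motor-on comparison within each woman is set up in the same way with or without an extra sentence.

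This rests on two assumptions: that the site obtains a scan report and a FRAX result before treating a woman as eligible, as the criteria demand, and that it does not accept verbal recall in their place. The overlap between the -2.5 and -2.49 cut-offs is a separate matter, and this conclusion does not depend on it.

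### Every woman has the motor-off control first and motor-on second, so a visit effect on the pre-to-post bone-marker change cannot be separated from vibration

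*Protocol*

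**What the plan says.** The Study Period section of the protocol sets one order for all women. At the first clinic visit the device is worn with the motor off. The second session is described as "visiting the clinic at the end of week one to measure acceleration, wear the device (motor on) for 30 minutes". Blood is drawn before and after activity at both visits.

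The Study Flow Outline labels the first session "Internal Control Acute assessment of bone marker with no vibration stimulus" and the second "Treatment Acute assessment of bone marker with 30 minute vibration". In both, the 30 minutes of activity are chosen by the woman, and the Study Period section allows standing or walking. Visit 1 also carries enrolment and consent.

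Under Trial Design the study is a "Single center prospective, non-randomized, unblinded, Non-Significant Risk (NSR) trial", with at most 24 women. The third item under Objectives is to demonstrate that women will "See changes in bone turnover". The Statistical Analysis section adds: "This study is observational, is not statistically powered and no formal statistical analyses are planned".

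The protocol describes no on-then-off sequence, no concurrent group without vibration and no second motor-off visit.

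**The concern.** The motor-off session is the only control for the bone-turnover objective, and it is always the first visit. Motor status and visit number therefore coincide for every woman. Anything that makes the pre-to-post marker change differ systematically between a first and a second visit is counted as vibration. Examples are the stress of a first visit, growing familiarity with the pack, or a tendency to choose a different activity the second time.

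The gap lies in the data that will be collected, so no analysis plan can close it afterwards. Nor does the lack of a formal test remove it: a listing of marker change by session, with one session labelled control and the other treatment, invites the on-versus-off reading and carries the same bias.

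Tolerability and delivered acceleration do not depend on the on-off contrast and are unaffected.

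**Working it through.** The protocol gives no effect size, SD, alpha or power, so there is no figure of its own to reproduce. The order of sessions, the four draws and the ceiling of 24 women come from the protocol. All effect sizes below are assumptions for illustration, in units of the SD of the within-woman on-off difference in marker change.

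**1. What the pre-activity draw removes.** Let D_v = post_v − pre_v at visit v. A constant shift in marker level at a visit enters both terms and cancels. An effect on the change itself does not.

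**2. Identifiability.** Model D_v with 24 woman effects, a visit effect and a motor effect, 26 columns in all.
- Fixed order: rank 25 of 26, and the correlation between visit and motor is 1.0. The two effects are fully aliased.
- 12 women off-then-on and 12 on-then-off: rank 26 of 26, correlation 0. The motor effect is estimable if there is no carry-over.

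**3. Bias.** Let τ be the vibration effect, π the visit effect on the change, and λ the carry-over of vibration into the change at a later control session.
- Fixed order: E[D2 − D1] = τ + π.
- Balanced order: the mean on-minus-off difference is τ + π in the off-then-on sequence and τ − π − λ in the other. Their average is τ − λ/2.

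With τ = 0 (20,000 simulated trials of 24 women agree with the algebra):

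| Assumed nuisance | Bias, fixed order | Bias, balanced order |
|---|---|---|
| Level shift 1.0 | 0.00 | 0.00 |
| π = 0.3 | 0.30 | 0.00 |
| λ = 0.3 | 0.00 | −0.15 |
| π = 0.3 and λ = 0.3 | 0.30 | −0.15 |

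In absolute size the balanced order is less biased when λ/2 < π, that is, when λ < 2π.

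**4. Precision (95% CI half-width).**
- Fixed order: t(0.975, n−1)/√n. This is 0.422 for n = 24 and 0.533 for n = 16.
- Balanced order with a and b women: t(0.975, n−2) × 0.5 × √(1/a + 1/b). This is 0.423 for 12:12, 0.425 for 11:13, 0.429 for 10:14, 0.449 for 8:16 and 0.536 for 8:8.

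The standard error with 24 women is the same either way: 1/√24 = 0.204, and √((1/12 + 1/12)/4) = 0.204.

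**5. How well carry-over could be checked.**
- Comparing pre-activity levels between sequences (two-sample t-test, 12 v 12, two-sided 5%) has power 0.216 for a 0.5 SD difference and 0.802 for 1.2 SD. It sees only carry-over in level, not in response.
- A comparison confined to visit 1 is free of carry-over, but its half-width is t(0.975, 22) × √(2/12) = 0.847 SD of a single-visit change.

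**The case against.** The best defence is that the protocol plans no on-off estimate and no test. It calls itself non-randomised and observational and intends only to list data, so no planned inference is invalid. That rightly limits the weight of the point. It does not dispose of it, because the protocol itself names a control session and a treatment session and sets out to demonstrate a change in bone turnover.

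Second, putting the control first keeps it free of earlier vibration. If the visit effect is zero and carry-over is not, the present order is unbiased and the balanced one is not. Neither quantity is in the protocol, and the carry-over check is weak. This stands as a real trade-off. Against it, the exposure is one 30-minute session about a week earlier and the marker assessment is described as acute. That makes large carry-over less of a worry without excluding it.

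Third, self-selected activity supports the concern only in part. Haphazard differences between visits are noise, and a change of activity prompted by the running motor follows the motor in either order. Only a systematic first-to-second-visit shift is cured by balancing. This is correct, but activity is one of several possible sources of a visit effect.

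Finally, the study is unblinded, so any effect of knowing that the motor is on remains under either order. That also stands.

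**Conclusion.** The concern holds. With a single off-then-on sequence, the on-off difference in pre-to-post marker change estimates vibration plus any visit effect on that change, and the collected data cannot divide the two. This follows from the design and needs no assumption about effect size.

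How large the bias is cannot be known from the protocol: it equals the visit effect, for which no size or direction is given. The preference for a balanced order assumes that carry-over is less than twice the visit effect. It costs almost nothing in precision (0.422 versus 0.423 SD with 24 women).

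The change is worth making but is not critical. It concerns one of three objectives, for which no formal test is planned.

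**What to change.** Randomise the order of the two sessions about 1:1 (off-then-on, on-then-off). Use small blocks, because 24 is a ceiling and enrolment may stop short of it. Keep the same gap between visits, take the acceleration measurement at whichever visit has the motor on, and amend the Trial Design entry to say that session order is randomised. Summarise the within-woman on-off difference in pre-to-post change by sequence and average the two sequence means, which is equivalent to fitting a visit term.

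The cost is a randomisation list and a short amendment, with no extra visits, draws or women. The amendment should acknowledge possible carry-over into the control session when vibration comes first, and that it can be checked only weakly.

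If the sponsor keeps the fixed order, add a sentence under Statistical Analysis saying that the on-off difference in marker change includes any visit effect and cannot be attributed to vibration alone. Under either order, the report should also say that the women knew whether the motor was running.

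### Objective 3 sets out to demonstrate changes in bone turnover and a motor-off control is built for it, but the analysis plan is a by-subject listing with no on-versus-off estimate

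*Protocol*

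**What the plan says.** The Objectives entry of the Protocol Summary opens with "To demonstrate that postmenopausal women will" and gives as its third item "See changes in bone turnover".

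The Study Flow Outline builds a within-woman comparison for that item. Office Visit #1 is labelled "Internal Control Acute assessment of bone marker with no vibration stimulus" and Office Visit #2 "Treatment Acute assessment of bone marker with 30 minute vibration". The Study Period section repeats the scheme. At the first visit each woman is "wearing the device (motor off) for 30 minutes while standing or walking, and completing a pre-post activity blood draw". At the second she does the same with the motor on, and acceleration is measured. Each woman therefore gives four blood samples.

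The Statistical Analysis entry reads: "This study is observational, is not statistically powered and no formal statistical analyses are planned". The output it describes is: "Data will be listed by subject; treatment number, and subject tolerability during treatment". The Number of Subjects entry sets a ceiling of 24, and the design is non-randomized and unblinded.

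**The concern.** A control session is useful only if the treatment session is compared with it. The paired draws exist so that the marker change with the motor on can be set against the change with the motor off, yet the analysis text does not commit to that comparison or to any summary of the marker. A reader of the listing could look at the motor-on change alone, compare the two post-activity samples, or choose another pairing, with no stated uncertainty in any case.

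The objective's verb makes this worse. To demonstrate a change is a stronger claim than an unblinded study with a fixed off-then-on order and self-selected activity can support, and a listing has no means of supporting it. At stake is whether the blood samples can answer, even in an exploratory way, the question for which they are drawn.

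**Working it through.** The protocol gives no power, significance level, effect size or SD, so there is no figure to reproduce. The check has three parts.

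**1. Objectives against planned output**

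| Objective | Data collected | Named in the Statistical Analysis entry? |
|---|---|---|
| 1. Tolerate the device | Questionnaires at both visits | Yes, tolerability |
| 2. Receive therapeutic vibration | Acceleration at the second visit | No |
| 3. Changes in bone turnover | Pre and post samples at both visits | No |

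Treatment number also appears in the listing sentence, but it is an identifier and not an outcome. No on-versus-off contrast is specified anywhere in the document.

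**2. Precision of the missing estimate**

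For each woman let D = (post − pre, motor on) − (post − pre, motor off). The 95% interval for the mean of D has half-width t(0.975, n−1)/√n, in units of the SD of D.

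- n = 24 (the protocol's ceiling): 2.069/4.899 = 0.42 SD
- n = 18 (assumed): 2.110/4.243 = 0.50 SD
- n = 12 (assumed): 2.201/3.464 = 0.64 SD

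The protocol gives no SD for the marker, so these cannot be turned into marker units.

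**3. What informal reading could show by chance**

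Assume no vibration effect and no visit effect, so each woman's D is equally likely to be up or down. The chance that at least k of n women move in the same direction, whichever it is, is 2 × P(X ≥ k) with X binomial(n, 0.5).

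| Pairs | Two-thirds or more | Chance | Three-quarters or more | Chance |
|---|---|---|---|---|
| 24 | 16 | 2 × 0.0758 = 15% | 18 | 2 × 0.0113 = 2% |
| 18 | 12 | 2 × 0.1189 = 24% | 14 | 2 × 0.0154 = 3% |
| 12 | 8 | 2 × 0.1938 = 39% | 9 | 2 × 0.0730 = 15% |

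The two cuts, and the 18 and 12 pairs, are assumptions. The table shows why a listing should be accompanied by an interval; it does not measure bias in this trial.

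**The case against.** The strongest reply is that this is an openly disclosed choice. The study is small, uncontrolled by randomization and declared unpowered, and a listing is a coherent output for such a study. The listing sentence is loosely punctuated and can be read as all data being listed by those keys, so marker and acceleration values may well be included. Saying that no formal analysis is planned does not rule out descriptive summaries. The session labels also signal which comparison is intended. Nothing suggests that conclusions would be drawn by counting directions, and the chance figure at 24 pairs falls from 15% to 2% with the choice of cut. Finally, the proposed estimate would itself be confounded, and an interval might lend it undue authority.

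Much of this is right. Lack of power is no fault, the marker values may be listed, and the direction counts are only illustrative. The labels do point to the natural contrast. But the analysis entry is not silent in a way that leaves detail to a later document: it states that there is no formal analysis and describes the output. A signal in a flow chart is not a commitment to an estimate. The confounding is real, but it affects a reading of the listing equally, and there no caveat is attached. It is a further reason to drop the word demonstrate. One more part of the reply stands: the protocol speaks only of a bone marker, so an estimate is fully prespecified only if the marker and its scale are named.

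**Conclusion.** The concern holds, as a minor one. Followed as written, the plan cannot support objective 3, because the protocol sets up a within-woman control and then specifies no comparison with it. The exact claim is that no on-versus-off estimate is planned in this protocol; it is not that marker data will go unreported.

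The estimate would be imprecise but usable as exploratory information, at 0.42 SD of the within-woman difference if all 24 women complete both visits. That rests on the ceiling being reached and on approximate normality of the mean difference. It says nothing about the systematic effects of visit order or activity, which no interval will show.

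**What to change.** Keep the statement that the study is not powered, and keep the listing. Then:

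- Add one prespecified exploratory estimate: the mean within-woman difference, motor on minus motor off, in pre-to-post bone marker change. Give a paired 95% confidence interval and the number of complete pairs, and make no claim of significance. Name the marker and the scale (absolute, percent or log).
- Print beside it that the fixed off-then-on order and the self-selected activity mean the contrast cannot be attributed to vibration alone.
- Summarise measured acceleration descriptively for objective 2.
- Replace demonstrate with estimate or explore in the Objectives entry. Doing this alone would remove the conflict of wording but would leave the control session without a planned use.

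The cost is a few sentences of protocol text and a few lines of analysis on data already collected, with no added visits, blood draws or subjects. The drawback is a wide interval that could be over-read as a vibration effect if the caveat is separated from it.
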